### 3.1.2 Second Study Visit [Hemlibra (emicizumab) Loading Doses]

The second study visit will take place at the IHTC up to 10 days after the initial screening visit. The purpose of the second study visit is to administer the 4 weekly loading doses of Hemlibra (emicizumab); acquire ADA data, vital signs (blood pressure, pulse, temperature, and respiratory rate) and weight; and complete baseline radiology.

Prior to the first loading dose, a banked plasma sample will be obtained to determine baseline anti-drug antibody levels for Hemlibra (emicizumab). Baseline radiology (CT and/or MRI) will also be obtained if not previously performed within one month of study entry or if provided scans are deemed inadequate to accurately assess the extent of the pseudotumor.

Subjects/caregivers will be instructed on how to inject Hemlibra (emicizumab) and how to recognize signs/symptoms of hypersensitivity (including anaphylaxis) and obtain emergency care in the event of such reactions occurring. The Study Investigator has the discretion to provide additional training or include additional observation (eg, after the fourth loading dose), if deemed appropriate, and each subject/caregiver will be able to ask any question he or she may have prior to being deemed capable of performing subcutaneous Hemlibra (emicizumab) injections. If, despite additional training, the investigator determines that the subject/caregiver is unable to inject Hemlibra (emicizumab), a trained and proficient caregiver or local healthcare provider should be identified to administer the prophylaxis injections.

The 4 loading doses will be administered once weekly for 4 weeks using the FDA-approved regimen (3 mg/kg once weekly by subcutaneous injection). Following the 4th loading dose a second banked plasma sample will be obtained to determine anti-drug antibody levels for Hemlibra (emicizumab). If the subject routinely uses an activity monitoring device and has consented to the use of data from that device during the study, then data from the time of informed consent will be collected.

During study visit 2 suitable quantities (to be determined by the Study Investigator) of Hemlibra (emicizumab) will be dispensed to the subject (see **Section 6.7**).

### 3.1.3 Subsequent Scheduled Study Visits

Subsequent study visits will occur once a quarter, as is the standard of care for patients with hemophilic pseudotumor. These study visits will take place at the medical facilities of the subject's local physician, except for the annual and study close-out visits, which will take place at the IHTC. The first subsequent study visit will be 3 months ( $\pm$ 2 weeks) following the first loading dose of Hemlibra (emicizumab).

The specific requirements of each visit are listed below. Depending on when a subject enrolls and when the study ends, the subject might not participate in all study visits beyond month 24. See **Appendix 2**.

*3.1.3.1 Study visits at months 3, 9, 15, 21, 27, 33, 39 and 45 ( $\pm 2$  weeks)*

The subject will follow-up with their local physician at the intervals specified above.

During this visit:

- Measurement of vital signs (blood pressure, pulse, temperature, and respiratory rate) and weight
- Review of patient diary for completeness
- Patient study documentation will be submitted to the IHTC for review of compliance and data collection
- Review of AEs
- Review of concomitant medications and supplements
- Data will be obtained from an activity monitoring device if standardly utilized by the patient (if applicable)

*3.1.3.2 Study visits at months 6, 18, 30 and 42 ( $\pm 2$  weeks)*

The subject will follow-up with their local physician for a more detailed clinical review at the intervals specified above.

During this visit the following data will be collected and/or reviewed and transmitted to the IHTC:

- Measurement of vital signs (blood pressure, pulse, temperature, and respiratory rate) and weight
- CBC panel w/diff
- Review of breakthrough bleeding events requiring alternate hemostatic therapy
- Review of the number of hospital admissions
- Review of the development of anemia requiring transfusion or intervention
- Review of AEs
- Review of concomitant medications and supplements
- Review of patient diary for completeness
- Patient study documentation will be submitted to the IHTC for review of compliance and data collection
- Data will be obtained from an activity monitoring device if standardly utilized by the patient (if applicable)

### *3.1.3.3 Annual study visits (months 12, 24 and 36 ±2 weeks)\**

The annual study visit will take place at the IHTC.

During this visit the following data will be collected and/or reviewed at the IHTC:

- Measurement of vital signs (blood pressure, pulse, temperature, and respiratory rate) and weight
- Radiologic evaluation (CT and/or MRI) to evaluate control of progression, stabilization or regression of pseudotumor
- Anti-drug antibodies (banked plasma sample)
- Repeated Haem-A-QoL and EQ-5D-5L
- CBC panel w/diff
- Review of breakthrough bleeding events requiring alternate hemostatic therapy
- Review of the number of hospital admissions
- Review of the development of anemia requiring transfusion or intervention
- Review of AEs
- Review of concomitant medications and supplements
- Review of patient diary
- Patient study documentation will be collected for review of compliance and data collection
- Data will be obtained from an activity monitoring device if standardly utilized by the patient (if applicable)

During this annual visit, a physical examination will be performed, used/empty vials of emicizumab will be collected and a suitable quantity of Hemlibra (emicizumab) will be dispensed (see **Section 6.7**).

### *3.1.3.4 Study close out visit*

See **Section 7.5**

## 3.1.4 Unscheduled Study Visits

Any unscheduled study visits with the subject's local hemophilia physician will be recorded in the CRF along with all relevant medical information (eg, reason for visit, diagnoses, scans, AEs, lab results, vital signs [blood pressure, pulse, temperature, and respiratory rate], weight, etc).

---

\* Subjects enrolled in the study for the maximum length of time (ie, 48 months) will also participate in an annual visit at approximately the 48-month time point; however, this will be the subject's close-out visit, and the procedures required will be those listed in **Section 7.5**. The primary difference between an annual visit and the close-out visit is the collection of used and unused vials of Hemlibra (emicizumab), rather than the dispensation of additional drug

If a subject meets with a physician other than their local hemophilia physician, that information should be communicated to their hemophilia physician at the next scheduled quarterly study visit and appropriate medical information recorded in the CRF.

Hospitalizations should be recorded in the CRF along with relevant medical information (see **Section 6.11.3.2d**). These should be reported to the IHTC within 7 days of their occurrence.

AEs should be reported using the instructions in **Section 6.11.3**.

### 3.1.5 Surgeries

All surgeries will be recorded in the CRF, which should minimally include the following information (see **Section 6.11.3** for additional reporting requirements):

- Procedure type
- Reason for procedure
- Planned or unplanned
- Date of procedure and length of hospitalization
- Hemostatic therapy provided pre-procedure (type, dose and dates)
- Hemostatic therapy provided post-procedure (type, dose and dates)
- Hemostatic outcome immediately post-procedure
- Hemostatic outcome at the end of hospitalization
- Adverse events experienced (including, but not limited to clots, thromboses and TMA)
- Vital signs (blood pressure, pulse, temperature, and respiratory rate) and weight

Hemostatic outcome for surgical treatment is defined using the standard ISTH rating scale shown below [Blanchette, Key et al. 2014].

Excellent	Intraoperative and postoperative blood loss similar (within 10%) to the non-hemophilic patient with no extra (unplanned) doses of FVIII/FIX/‘bypassing agents’ needed and blood component transfusions are similar to the non-hemophilic patient
Good	Intraoperative and/or postoperative blood loss slightly increased over expectation for the non-hemophilic patient (between 10 and 25% of expected), but the difference is judged by the involved surgeon/anesthetist/relevant healthcare professional to be clinically insignificant as evidenced by no extra (unplanned) doses of FVIII/FIX/‘bypassing agents’ needed and blood component transfusions are similar to the non-hemophilic patient
Fair	Intraoperative and/or postoperative blood loss increased over expectation (25–50%) for the non-hemophilic patient and additional treatment is needed such as extra (unplanned) doses of FVIII/FIX/‘bypassing agents’ or increased blood component use (within two-fold) of the anticipated transfusion requirement

Poor	Significant intraoperative and/or postoperative blood loss that is substantially increased over expectation (> 50%) for the non-hemophilic patient, requires intervention, and is not explained by a surgical/medical issue other than hemophilia, unexpected hypotension or unexpected transfer to an Intensive Care Unit due to bleeding or substantially increased blood component use (>2 fold) of the anticipated transfusion requirement
------	--

Medical details and outcome of all surgeries should be reported to the IHTC within 7 days of their occurrence.

### 3.1.6 Subject Withdrawal/Study Termination Procedures

See **Section 7.6**

### 3.1.7 Follow-up Period

No follow-up period is planned with the exception of post-study adverse events listed in **Sections 6.11.2.1 and 6.11.3.2g**.

## 3.2 Rationale for Study Design

Hemophilic pseudotumor is a complication of hemophilia (1-2% of patients) that consists of a progressive cystic swelling of muscle and/or bone caused by recurrent hemorrhage. It is observed more frequently in geographic areas where hemophilia is diagnosed late, treatment is inconsistently available, prophylaxis is not used due to resource constraints, and in patients who do not recognize that a bleeding event has occurred (eg, moderate or mild deficient patients who experience a bleed/injury). FVIII prophylaxis has been used in patients with hemophilia A with pseudotumors when surgical intervention is not feasible either due to lack of local expertise or inability to perform the intervention due to extent or site of the pseudotumor. Pseudotumors may be present in patients with hemophilia either with or without an inhibitor and are more common in patients with inhibitors where hemostasis is less well controlled.

It is hypothesized that an agent that confers a consistent FVIII level in the mild deficient range that is not associated with trough levels below 10% will confer a higher degree of hemostasis in patients with pseudotumors; this will result in a decreased rate of breakthrough bleeding requiring intermittent hemostatic therapy, and an associated decrease in uncontrolled bleeding resulting in anemia, transfusion, and hospitalization. If these endpoints are achieved it is also hypothesized that activity and quality of life may increase or improve respectively.

The purpose of this study is to prospectively investigate the hemostatic efficacy and safety of weekly prophylactic Hemlibra (emicizumab) in the treatment/control of pseudotumors in children and adults with FVIII deficiency (baseline FVIII level <40%) either with or without an inhibitor; in addition, changes in quality of life and activity level in subjects with hemophilia A and pseudotumor will be assessed.

### **3.3 Study Duration and Dates**

The enrollment period for this study will last 2 years and is planned to start in the first quarter of 2019.

Each subject will receive Hemlibra (emicizumab) therapy for a minimum of 2 years unless they voluntarily withdraw, are involuntarily withdrawn by the Study Investigator, or the study is terminated early. The maximum duration of Hemlibra (emicizumab) therapy on study is 4 years. The maximum time on study for each subject is dependent on when they enroll.

The study will last a maximum of 4 years from the date of the first signed consent form from the first subject, to the last administration of Hemlibra (emicizumab) to any subject.

## 4 STUDY POPULATION SELECTION

### 4.1 Study Population

Approximately 10 subjects will be enrolled in this study and receive study medication. There are no restrictions on weight or BMI.

### 4.2 Inclusion Criteria

Patients must meet the following criteria for study entry:

- Signed informed consent form from the subject, parent or guardian
- Diagnosis of congenital hemophilia A (baseline FVIII level <40%) with or without FVIII inhibitor, either high or low responding, regardless of titer
- Diagnosis of a hemophilic pseudotumor confirmed by radiologic assessment such as CT or MRI
- Any weight or BMI
- Medical documentation of prophylactic or episodic treatment (FVIII or bypassing agent) and the number of bleeding episodes for at least 16 weeks, and up to 6 months if available, prior to entry into the study
- Medical documentation of any need for PRBC transfusion or hospitalization for 6 months prior to entry into the study
- Subjects with a history of an inhibitor should provide documentation of the inhibitor history including date of initial diagnosis of inhibitor, peak titer, and agent utilized for hemostatic control
- Subjects with high titer inhibitors or those with low titer inhibitors who do not respond to FVIII must be willing to use rFVIIa as first line therapy for the treatment of breakthrough bleeding events
- Medical documentation of ITI therapy for subjects with a history of a FVIII inhibitor and ITI, including current FVIII inhibitor titer
- Willingness to discontinue any current prophylactic hemostatic regimen (FVIII or bypassing agent) and/or FVIII ITI therapy for the duration of the study
  - Subjects receiving FVIII prophylaxis must be willing to discontinue their FVIII prophylactic regimen immediately prior to their second loading dose of Hemlibra (emicizumab)
  - Subjects receiving bypassing agent prophylaxis must be willing to discontinue their prophylactic regimen at least 24 hours prior to their first loading dose of Hemlibra (emicizumab)

- Subjects receiving FVIII ITI therapy must be willing to discontinue ITI immediately prior to their first loading dose of Hemlibra (emicizumab)
- Willingness and ability to comply with scheduled visits, treatment plans, laboratory tests, and other study procedures, including the health-related questionnaires, activity tracking, and bleed diaries, using systems provided during the study
- Adequate hepatic function, defined as total bilirubin  $\leq 1.5 \times$  age-adapted upper limit of normal (ULN) (excluding Gilbert's syndrome) and both AST and ALT  $\leq 3 \times$  age-adapted ULN at the time of screening, and no clinical signs or known laboratory/radiographic evidence consistent with cirrhosis
- Subjects must be willing to be vaccinated against HAV and HBV if not previously vaccinated, exposed or immune to HAV or HBV\*
- Adequate hematologic function, defined as a platelet count  $\geq 100,000/\mu\text{L}$  and a PT  $\leq 1.5$  times the ULN at the time of screening
- Adequate renal function, defined as serum creatinine  $\leq 2.5 \times$  age-adapted ULN and creatinine clearance  $\geq 30 \text{ mL/min}$  by Cockcroft-Gault formula
- For women with hemophilia of childbearing potential: agreement to remain abstinent (refrain from heterosexual intercourse) or use highly effective contraceptive methods that result in a failure rate of  $<1\%$  per year during the treatment period and for at least 5 elimination half-lives (24 weeks) after the last dose of study drug

#### 4.3 Exclusion Criteria

Subjects who meet any of the following criteria will be excluded from study entry:

- Inherited or acquired bleeding disorder other than congenital hemophilia A
- Lack of a documented diagnosis of hemophilic pseudotumor
- Patients who are at high risk for TMA (eg, have a previous medical or family history of TMA), in the Study Investigator's judgment
- History of illicit drug or alcohol abuse within 48 weeks prior to screening, in the Study Investigator's judgment
- Previous (within the last 12 months) or current treatment for thromboembolic disease (with the exception of previous catheter-associated thrombosis for which anti-thrombotic treatment is not currently ongoing) or signs of thromboembolic disease
- Other conditions (eg, certain autoimmune diseases) that may currently increase the risk of bleeding or thrombosis

---

\* Vaccinations will not be charged to the study.

- History of clinically significant hypersensitivity associated with monoclonal antibody therapies or components of the Emicizumab injection
- Planned surgery (excluding minor procedures such as tooth extraction or incision and drainage) during the study
- Known HIV infection with CD4 counts <200 cells/ $\mu$ L. HIV infection with CD4 counts  $\geq$ 200 cells/ $\mu$ L permitted
- Use of systemic immunomodulators (eg, interferon) at enrollment or planned use during the study, with the exception of anti-retroviral therapy
- Concomitant disease, condition, significant abnormality on screening evaluations or laboratory tests, or treatment that could interfere with the conduct of the study, or that would, in the opinion of the Study Investigator, pose an additional unacceptable risk in administering study drug to the patient
- Receipt of any of the following:
  - Hemlibra (emicizumab) in a prior investigational study
  - An investigational drug to treat or reduce the risk of hemophilic bleeds within 5 half-lives of last drug administration
  - A non-hemophilia-related investigational drug within last 30 days or 5 half-lives, whichever is shorter
  - Any other investigational drug currently being administered or planned to be administered
- Inability to comply with the study protocol in the opinion of the Study Investigator
- Pregnancy or lactation or intention to become pregnant during the study
- Women with a positive serum pregnancy test result within 10 days prior to initiation of study drug

## 5 STUDY TREATMENT(S)

### 5.1 Description of Treatment(s)

#### 5.1.1 Study Drug

The study drug is US-labeled Hemlibra (emicizumab). It will be administered using the FDA approved once-weekly dosing regimen for loading dose (3 mg/kg) and prophylactic dose (1.5 mg/kg, or 3 mg/kg kg if dose escalation is determined appropriate by the Study Investigator). Hemlibra (emicizumab) will be provided in a clear vial as a solution. Hemlibra (emicizumab) will be provided by the study.

#### 5.1.2 Non-study Drugs

Should a breakthrough bleed occur, then any locally approved pdFVIII or rFVIII may be used in subjects without a FVIII inhibitor or with a low titer inhibitor (titer <5BU) using the local standard of care; if the subject's standard of care for treatment of bleeding events with low titer inhibitors is a bypassing product, the subject will follow treatment as outlined under high titer inhibitors (below).

Should a breakthrough bleed occur in subjects with a high titer FVIII inhibitor (titer  $\geq$ 5BU), then any locally approved rFVIIa concentrate may be used using the local standard of care. Other bypassing agents (eg, aPCC) may only be used with the approval of the Study Investigator. Agents to treat breakthrough bleeds or other sequelae (including, but not limited to pdFVIII, rFVIII, rFVIIa, and aPCC) will not be provided by the study.

### 5.2 Packaging and Labeling

US-labeled Hemlibra (emicizumab) will be supplied as a solution in clear glass vials at nominal doses of 30mg, 60mg, 105mg and 150mg. Vials will be packaged in an outer box. In addition, supplies for administration of Hemlibra (emicizumab) will be provided (eg, syringes, transfer needles, injection needles, alcohol wipes, etc).

### 5.3 Treatments Administered

#### 5.3.1 Loading Doses of Hemlibra (emicizumab)

After obtaining informed consent and the performance of screening procedures, patients who (at the discretion of the Study Investigator) meet all inclusion and exclusion will be eligible for study medication.

The 4 loading doses of Hemlibra (emicizumab) will be administered as 3 mg/kg subcutaneous injections, dosed once-weekly over a 4-week period during study visit 2 (**Section 7.2**).

### 5.3.2 Prophylactic Doses of Hemlibra (emicizumab)

Prophylactic administration of Hemlibra (emicizumab) will continue on a weekly basis (1.5 mg/kg subcutaneous dosing, or 3 mg/kg kg if dose escalation is determined appropriate by the Study Investigator [Section 5.3.3]) until the subject withdraws from the study, is involuntarily withdrawn from the study, or the study is terminated, whichever occurs first (Section 7.3). All used and unused vials of Hemlibra (emicizumab) should be returned to the IHTC once a subject is no longer enrolled.

### 5.3.3 Dose Escalation of Prophylactic Hemlibra (emicizumab)

*All subjects with suboptimal control of bleeding as defined by the protocol will be offered the option to increase their Hemlibra (emicizumab) maintenance dose to 3 mg/kg QW, with approval from the Study Investigator. Suboptimal response is defined as follows:*

- Two qualifying bleeds within 24 weeks while on prophylactic Hemlibra (emicizumab)

*A qualifying bleed is defined as spontaneous, verified by an investigator (eg, by imaging or physical examination or reliable symptoms reported by patient including increased pain with swelling, decreased ability to function etc clearly related to presence/site of pseudotumor), and occurring while on prophylactic Hemlibra (emicizumab) at steady state (after week 5). If the investigator believes that a specific subject warrants dose escalation on the basis of a different reason, he or she may discuss the case with the Study Investigator for consideration and potential approval.*

*If this 3 mg/kg maintenance dose does not result in increased control of breakthrough bleeding, the subject may return to the standard 1.5 mg/kg maintenance dose upon approval of the Study Investigator, assuming this 1.5 mg/kg dose had resulted in an improvement in breakthrough bleeding compared to their pre-study regimen.*

## 5.4 Treatment of Breakthrough Bleeds and Concomitant Therapies

No pdFVIII, rFVIII, rFVIIa or aPCC shall be administered unless required to treat a breakthrough bleed. **The use of aPCC should be avoided and may only be administered if approved by the Study Investigator. The use of any bypassing agent, other than rFVIIa (eg, NovoSeven®), requires approval of the Study Investigator.**

Drugs intended to control or prevent bleeds, including bypassing agents, should be used at the lowest dose expected to achieve hemostasis according to the local standard of care. Given that circulating Hemlibra (emicizumab) may increase the patient's coagulation potential, the usual doses of hemostatic medication (ie, bypassing agents, FVIII, antifibrinolytics, etc) required to achieve hemostasis may be lower than the doses used prior to starting Hemlibra (emicizumab). Use of aPCC in combination with Hemlibra (emicizumab) should be avoided in patients who have the option of using other bypassing agents to treat bleeds. In the event that aPCC is the only available bypassing agent, the lowest dose expected to achieve hemostasis should be prescribed,

with no more than 50 U/kg aPCC to be administered as an initial dose. The total dose of aPCC must be <100 U/kg/day for preferably less than 1 day. **aPCC may only be administered if approved by the Study Investigator and may only be administered by a physician.**

Caution should be taken for patients who are using rFVIIa (eg, consideration of using no more than 90 µg/kg of rFVIIa as an initial dose). Other bypassing agents should be avoided. In cases where such agents are the only available bypassing agent, the lowest dose expected to achieve hemostasis should be prescribed, with no more than the lowest dose described in the prescribing information to be administered as an initial dose. **Bypassing agents other than rFVIIa may only be administered if approved by the Study Investigator.**

The exact dose and schedule of bypassing agents should be discussed with subjects at the beginning and throughout the study. Repeated dosing of rFVIIa, aPCC, or other bypassing agents should be performed only under medical supervision, which could include laboratory monitoring by additional local and central laboratory assessments, and consideration should be given to verifying bleeds prior to repeated dosing.

Caution should be taken if antifibrinolitics are used in conjunction with bypassing agents including rFVIIa and aPCC in patients receiving Hemlibra (emicizumab). Use of antifibrinolitics after one dose of bypassing agent (eg, as done for dental extractions) is allowed; concomitant use of rFVIIa and antifibrinolitics should be avoided if at all possible and concomitant use of aPCC and antifibrinolitics is not allowed. (see Restrictions, **Section 5.5**)

Drugs and therapies to treat AEs and use of topical antiseptics, anesthetics, eye drops, etc, that are not considered to result in systemic exposure are permitted.

All concomitant medications need to be registered in the subject's medical files and the patient diaries and recorded in the CRF.

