## 5.5 Restrictions

Use of the following therapies may be prohibited for subjects enrolled in ongoing studies and for at least 4 weeks prior to the initiation of study treatment.

- Use of drugs that would affect hemostasis (eg, aspirin, non-steroidal anti-inflammatory drugs, or anticoagulants [other than to flush, dwell, or de-clot a central venous access device]) but excluding drugs intended to control bleeding episodes or used in the context of minor surgery (eg, tooth extraction) or injuries (eg, concussion) to prevent deterioration
- Use of systemic immunomodulators (eg, rituximab, interferon) other than antiretroviral therapy from enrollment to last observation
- Elective surgery (excluding minor procedures such as tooth extraction, central venous access device removal, or incision and drainage as well as emergency surgeries) from enrollment to last observation

- Use of aPCC for short-term or long-term prophylaxis
- Use of antifibrinolytics concomitantly with aPCC
- Use of other investigational drugs from enrollment to last observation

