#### 7.4.5 Surgeries

All surgeries will be recorded in the CRF, which should minimally include the following information (see **Section 6.11.3** for additional reporting requirements):

- Procedure type
- Reason for procedure
- Planned or unplanned
- Date of procedure and length of hospitalization
- Hemostatic therapy provided pre-procedure (type, dose and dates)
- Hemostatic therapy provided post-procedure (type, dose and dates)
- Hemostatic outcome immediately post-procedure
- Hemostatic outcome at the end of hospitalization
- Adverse events experienced (including, but not limited to clots, thromboses and TMA)
- Vital signs (blood pressure, pulse, temperature, and respiratory rate) and weight

Hemostatic outcome for surgical treatment is defined using the standard ISTH rating scale shown below [Blanchette, Key et al. 2014].

Excellent	Intraoperative and postoperative blood loss similar (within 10%) to the non-hemophilic patient with no extra (unplanned) doses of FVIII/FIX/‘bypassing agents’ needed and blood component transfusions are similar to the non-hemophilic patient
Good	Intraoperative and/or postoperative blood loss slightly increased over expectation for the non-hemophilic patient (between 10 and 25% of expected), but the difference is judged by the involved surgeon/anesthetist/relevant healthcare professional to be clinically insignificant as evidenced by no extra (unplanned) doses of FVIII/FIX/‘bypassing agents’ needed and blood component transfusions are similar to the non-hemophilic patient
Fair	Intraoperative and/or postoperative blood loss increased over expectation (25–50%) for the non-hemophilic patient and additional treatment is needed such as extra (unplanned) doses of FVIII/FIX/‘bypassing agents’ or increased blood component use (within two-fold) of the anticipated transfusion requirement
Poor	Significant intraoperative and/or postoperative blood loss that is substantially increased over expectation (> 50%) for the non-hemophilic patient, requires intervention, and is not explained by a surgical/medical issue other than hemophilia, unexpected hypotension or unexpected transfer to an Intensive Care Unit due to bleeding or substantially increased blood component use (>2 fold) of the anticipated transfusion requirement

Medical details and outcome of all surgeries should be reported to the IHTC within 7 days of their occurrence.

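### The opening rule of Section 5.4 allows FVIII, rFVIIa and aPCC only to treat a breakthrough bleed, which leaves no room for the peri-procedural cover that the rest of the protocol expects

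*Combined protocol and SAP*

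**What the plan says.** The governing sentence is the first one in Section 5.4: "No pdFVIII, rFVIII, rFVIIa or aPCC shall be administered unless required to treat a breakthrough bleed". It covers all four product types, gives one permitted reason and states no exception.

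Section 5.1.2 describes the same products in the setting of a bleed, for example "Should a breakthrough bleed occur, then any locally approved pdFVIII or rFVIII may be used in subjects without a FVIII inhibitor". It places rFVIIa for high-titer inhibitor subjects in the same setting.

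Procedures are allowed on study. Section 4.3 excludes planned surgery but not minor procedures. Section 5.5 lists as restricted "Elective surgery (excluding minor procedures such as tooth extraction, central venous access device removal, or incision and drainage as well as emergency surgeries", so minor procedures and emergency operations fall outside that restriction.

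Other text expects hemostatic agents around those procedures:

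- Section 5.4, on dosing: "Drugs intended to control or prevent bleeds, including bypassing agents, should be used at the lowest dose expected to achieve hemostasis".
- Section 5.4, on antifibrinolytics: "Use of antifibrinolitics after one dose of bypassing agent (eg, as done for dental extractions) is allowed".
- Sections 3.1.5 and 7.4.5, the top category of the surgical rating scale: "Intraoperative and postoperative blood loss similar (within 10%) to the non-hemophilic patient with no extra (unplanned) doses of" FVIII, FIX or bypassing agents.
- The same sections, among the items to be recorded for every surgery: "Hemostatic therapy provided pre-procedure (type, dose and dates".
- Sections 2.2, 6.10.2 and 9.6: use of FVIII, rFVIIa or aPCC at surgery is a secondary objective and a secondary endpoint.

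Sections 7.2 and 7.2.3.1 have subjects on FVIII prophylaxis stop it immediately before the second loading dose (Day 7), not before the first.

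**The concern.** Local physicians carry out most quarterly visits and choose the FVIII product, so they need a rule they can apply without interpretation. As written, a dose of FVIII or rFVIIa given before a tooth extraction, with no bleed present, has no permitted reason. The physician must either withhold it from a patient with hemophilia or give it and incur a protocol deviation. A record of surgical use under the secondary endpoint would then consist partly of deviations from the protocol's own treatment rule.

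This is a wrongly stated rule, not a missing detail: the sentence is explicit, and other explicit parts of the protocol contradict it.

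**Working it through.** The plan states no figure on this point, so the check is a comparison of texts, followed by one line of arithmetic on exposure.

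**1. How strict is the rule?** The first sentence of 5.4 is a prohibition with a single condition. Section 5.1.2 is different in kind. It says what may be used if a bleed occurs, has no exclusive wording for FVIII or rFVIIa, and refers to agents for other sequelae as well as bleeds. There is one ban, in 5.4, and 5.1.2 is context for it.

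**2. Which statements contradict it?**

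| Text | What it implies | Weight |
|---|---|---|
| 5.4, dental extraction example | A bypassing dose whose stated occasion is the procedure, not a bleed | Strong; same section as the ban |
| 5.4, drugs to control or prevent bleeds | Preventive use of hemostatic agents, with dosing guidance | Strong; same section |
| 2.2, 6.10.2, 9.6, use at surgery | FVIII, rFVIIa and aPCC are expected at operations and will be evaluated | Strong on intent; does not by itself separate preventive from therapeutic doses |
| 3.1.5 and 7.4.5, rating scale | Excellent and Good require no unplanned doses, so planned doses are presupposed | Moderate; a standard published scale, adopted without change |
| 3.1.5 and 7.4.5, pre-procedure therapy item | Therapy may be given before the procedure | Weak alone; the entry could be an antifibrinolytic or none |

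**3. Does Section 5.5 resolve it?** One item there exempts drugs used at minor surgery or after injury to prevent deterioration. That exemption belongs to a list introduced by "Use of the following therapies may be prohibited for subjects enrolled in ongoing studies". Being exempt from a list of things that may be prohibited does not lift a separate mandatory ban. The exemption also names minor surgery and injuries, not emergency surgery. It shows what the authors meant, and so supports rewording 5.4.

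**4. Is every operation already bleed treatment?** No. A pre-procedure dose precedes any procedural bleeding. Section 6.11.2.2 lists emergent surgery for pseudotumor expansion as an alternative to uncontrolled bleeding. An operation for active bleeding is covered by the rule; one for expansion is not clearly covered.

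**5. The loading period.** Sections 7.2 and 7.2.3.1 allow FVIII prophylaxis between the first loading dose (Day 0) and the second (Day 7). The opening sentence of 5.4, read literally, forbids it.

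**6. Exposure.** Section 4.1 gives about 10 subjects and Section 3.3 gives 2 to 4 years each: 10 × 2 = 20 and 10 × 4 = 40 subject-years. No procedure rate is given, so this bounds exposure and does not count affected procedures.

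**The case against.** The best defense is that a clinician who reads 5.4 and 5.5 together would see the dental extraction example and the minor-surgery exemption, take the opening sentence as a bar on continued routine prophylaxis, and give cover. A protocol that makes surgical use an endpoint is also unlikely to be applied as forbidding it. In an emergency, Sections 8 and 10.2 let the investigator depart from the protocol to remove an immediate hazard. Pseudotumor expansion may often be a bleed in any case, because the protocol describes these lesions as caused by recurrent hemorrhage.

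Much of this stands as an argument about likelihood: withholding will be uncommon, especially in emergencies. It does not remove the contradiction. A routine extraction is not an immediate hazard, and cover given there still breaches the sentence as written.

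A reader might also infer that 5.1.2 is a second prohibition. The documents do not support that, for the reasons in step 1 of the working. Another tempting inference is that preventive doses would inflate the primary bleed rate. Sections 6.10.1 and 9.5 count breakthrough bleeding events that require therapy, so a preventive dose without a bleed is not an event. Misclassification would require a recording error, and the documents give no basis for assuming one.

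**Conclusion.** The contradiction is real and should be corrected. The first sentence of 5.4 conflicts with two later statements in its own section, with the surgical rating scale, with the secondary objective and endpoint on surgical use, and with the prophylaxis stop rule in 7.2. No text reconciles them.

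The practical effect is limited to care and deviation handling at permitted minor procedures and, less often, emergency surgery. The number is probably small, because planned non-minor surgery is excluded. That is a judgment over 20 to 40 subject-years with no stated procedure rate. The primary analysis and sample size are unaffected. Confidence is high on the textual conflict and lower on how often anyone would act on the literal wording.

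**What to change.** Replace the opening sentence of 5.4 with wording such as: *pdFVIII, rFVIII and rFVIIa may be given only (a) to treat a breakthrough bleed, (b) for peri-procedural hemostasis at a minor procedure or emergency surgery permitted under Section 5.5, or (c) in the case of FVIII, as existing prophylaxis until its scheduled stop under Section 7.2.*

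Handle aPCC in its own sentence: *aPCC must not be given as prophylaxis. At surgery it may be given only to treat bleeding, with Study Investigator approval and within the dose limits of this section.* This belongs in 5.4 because the aPCC item in 5.5 sits under the weaker introductory wording. It also keeps the mention of aPCC in the surgical objective and endpoint consistent with the treatment rule.

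A matching sentence in 5.1.2 is optional. A line in Section 9 saying that preventive procedural doses are reported under the surgical endpoint and are not breakthrough bleeds would be a clarification only.

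The cost is one sentence replaced by two, in an amendment needing IRB approval, with no change to visits, sample size or the primary analysis.
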